2. STUDY DESIGN

An analytical, longitudinal, experimental, prospective, controlled and randomized clinical study will be conducted to analyze the cause-effect relationship of the Müller & Puig physiotherapy protocol under study in relation to the change in pain, functionality (modified Harris scale) and the range of mobility (ROM) in subjects surgically operated by Femoro-acetabular Impingement (FAI) by arthroscopy.

The study will be simple blind with blinded evaluator strategy with two parallel groups. The surgeons (recruitment) and assessors will be blinded with respect to the group belonging to the subject. The statistician will be blinded to the subjects group until the statistical analysis is completed. It is not possible to blind the physiotherapist who executes the treatment protocol or the study subjects. Subjects will be asked not to disclose their membership group or consult with the surgeon or the evaluator.

The randomization approach will be prepared by means of a randomization computer program, attributing a 1:1 ratio to the membership group. The interventionist physiotherapist will perform the randomization on the day of the first post-surgery physiotherapy session.

All participants will be informed of the purpose of the study through an information document prepared for this purpose and will be clarified any doubts that may arise. After answering as many questions as necessary, the subject must sign the informed consent document to be part of the study. The principles of the Declaration of Helsinki (2004) will

be respected at all times. The data collected will be treated confidentially by applying the current legislation on the protection of personal data (Organic Law 15/1999 of December 13, Protection of Personal Data) and / or any other applicable.

This study has been admitted by the Research and Ethics Committee of General University Hospital of Elche PI 6/2019.

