5. STUDY VARIABLES

5.1. Independent variables study object

The independent variables of the project are: a) belonging to the control or intervention group; and b) time, according to the timing of presurgical and postsurgical measurements. We also recorded as independent variables the general characteristics of the sample: age, BMI, sex, hours of weekly sports activity, orthopedic surgeon who performed the intervention and compliance with the program.

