5.2. Dependent variables

The dependent variables of the study are the following:

Range of Mobility (ROM).

In the present study measurements will be made by goniometry of hip joint movement ranges. The goniometry is a technique of measurement of the angles created by the intersection of the longitudinal axes of the bones at the level of the joints.

These are continuous quantitative variables, measured in degrees with a range between 0° and 180°.

- a. ROM in hip flexion.
- b. ROM in hip extension.
- c. ROM in hip abduction.
- d. ROM in hip adduction.
- e. ROM in internal hip rotation.
- f. ROM in external rotation of the hip.

Orthopedic tests

The FAI will be checked through the performance of the Fabere, Fadir and Ober functional tests described below.

- a. **FABERE TEST:** The patient's hip is flexed, abducted and externally rotated by placing the external malleolus on the knee of the contralateral leg. The pelvis is

- stabilized and an overpressure is applied to the inside of the knee. It is positive if the pain in the buttock or groin is reproduced. Test with inter-evaluator reliability in Kappa values (95% CI) of 0.60.
- b. FADDIR TEST: Flexion, adduction and internal rotation test. The supine patient, the evaluator patiently brings the patient's hip up to 100° flexion and adduction while applying internal rotation. It is positive if pain in the groin is reproduced. Test with inter-evaluator reliability in Kappa values of 0.48.
 - c. OBER TEST: Patient in lateral decubitus position. The evaluator flexes the knee that is evaluated at 90° and abducts and extends the hip until it is level with the trunk. The evaluator lets the gravity bring the hip on adduction as possible. Test with inter-evaluator reliability of 0.90.

Variable intensity of pain

The Visual Analogue Scale (VAS) will be used. It is a continuous quantitative variable with a range between 0 and 10.

Evaluation functionality.

The modified Harris Scale will be used to the patient to evaluate the functionality of the hip and its interference in the activities of daily life. The patient will be evaluated with this scale prior to the surgical intervention and 14 weeks after the surgery.

6. STUDY GROUPS.

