B. Pre-surgery evaluation: the Harris scale questionnaire modified prior to the surgical procedure will be completed. After signing the informed consent, the pre-surgical measurement will be carried out following the following sequence:

- Assessment tests of abduction, adduction, flexion, extension, internal rotation and external rotation ROM of the hip
- Next, the Ober, Fabere and Faddir muscle tests will be performed.
- Finally, the pain will be evaluated through the Visual Analog Scale (VAS)

C. Randomization: After the presurgical evaluation and following a simple randomization process by means of a computer program, the subjects are assigned to the control or intervention group.

D. Hip arthroscopy: The study subjects will receive adequate pre- and postoperative care including health education and exercise plan for the immediate postoperative period, in addition to a follow-up visit by the traumatologist after two weeks of the intervention.

E. Intervention: The subjects of the control group follow the general postsurgical treatment protocol described by Gocen et al. The subjects of the intervention group will perform a physiotherapy session of 45 minutes each one every two weeks for a total of 7 sessions (weeks 2, 4, 6, 8, 10, 12 and 14 post surgery) following the protocol described. In addition, they will have to follow a physiotherapy exercise plan at home whose compliance they will have to register in an activity diary to check adherence to treatment.

F. Post-surgery evaluation 1: The evaluation described in section B and C is repeated 4 weeks after surgery to subjects of both groups.

G. Post-surgery evaluation 2: The evaluation described in section B and C is repeated after 14 weeks of the surgery for the subjects of both groups, and the individual study is finished.

In both groups, it will be advised to avoid stairs, ramps, squats, forced hip flexion and legs crossing in all phases. The subjects that develop a deterioration in the Modified Harris scale or in the VAS at 4 weeks after surgery compared with the pre-surgical data or those subjects that reflect complications of the surgery will be evaluated again by their corresponding traumatologist to decide whether or not to remain in the program. All complications will be documented by the principal investigator. No adverse effects are expected.

Statistical Analysis Plan (SAP)

Size Sample and Feasibility

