- d. For the comparison of means between the results of both groups we will use the t-Student test of related samples and one-way ANOVA (when they are normal) or Mann-Whitney U test or Wilcoxon W test (when they do not meet the normal).
- e. Chi square test or ANCOVA to analyze the influence of the general characteristics of the sample on the effect of the intervention.
- f. For the reliability analysis of the measuring tools, Cronbach's alpha test will be used.
- g. Regression analysis using the multiple linear model to study the relationship between sets of variables.

A significance index of $p < 0.05$ will be established.

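### Item d of the SAP assigns a related-samples t-test to the comparison of two independent arms, and does not fix the visit, the outcome metric or the use of the pre-surgery value

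*Combined protocol and SAP*

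**What the plan says.** Section 2 describes the design: "The study will be simple blind with blinded evaluator strategy with two parallel groups". Section 8, step C, gives the allocation method, "following a simple randomization process by means of a computer program", and no matching is mentioned anywhere.

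The SAP item that compares results between arms is item d of the inferential analysis: "For the comparison of means between the results of both groups we will use the t-Student test of related samples and one-way ANOVA" when data are normal, and Mann-Whitney U or Wilcoxon W otherwise.

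Three other places bear on what should be compared:

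- Section 2 frames the aim as the effect of the protocol "in relation to the change in pain, functionality (modified Harris scale) and the range of mobility (ROM").
- Section 5.1 lists as an independent variable "time, according to the timing of presurgical and postsurgical measurements".
- Section 7 sets three measurement times: before surgery, week 4 and week 14.

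ANCOVA appears only in item e. Its purpose there is to study the influence of "the general characteristics of the sample: age, BMI, sex, hours of weekly sports activity", together with surgeon and compliance (the list in section 5.1). The pre-surgery outcome value is not in that list. Item g names a multiple linear model without outcome or covariates.

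**The concern.** Item d carries the general objective, the effectiveness of the physiotherapy protocol. Two things are wrong with it.

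First, a related-samples t-test needs a natural partner for each observation. Subjects in one arm have no partner in the other. Read instead as before-versus-after within an arm, the test answers a different question. Both arms undergo arthroscopy, so both may improve whatever the physiotherapy does. The plan does not restrict within-arm results to description, so a gain after surgery could be read as a physiotherapy effect.

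Second, the valid tests in item d still leave several analyses open: week 4 or week 14, raw value or change, adjusted for baseline or not. These have different power and can give different verdicts on the same data. The pre-surgery outcomes are collected, yet no item clearly puts them into the between-arm comparison.

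**Working it through.** **Inputs from the documents.** About 30 per arm (SAP, sample size and feasibility); significance at p < 0.05, taken as two-sided; two arms, 1:1, simple randomisation (sections 2 and 8). The documents give no effect size, SD or correlation, so there is no planned power figure to reproduce.

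**Assumptions.** Outcome SD = 1 at each visit; pre-post correlation r = 0.3, 0.5, 0.7; shared gain after surgery of 0.5 or 0.8 SD; true between-arm difference d = 0.6 SD.

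**1. Pairing across arms.** A paired test on all subjects needs equal arms. With 60 subjects allocated by simple randomisation, P(30:30) = C(60,30)/2^60 = 0.103. The SAP also lets the 10 pilot subjects, all in one group, join the final sample. With 10 fixed in one arm and 50 randomised, P(30:30) = C(50,20)/2^50 = 0.042.

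**2. Within-arm use, no true difference between arms.** The SD of change is √(2(1−r)) = 1.183/1.000/0.775. The paired t-test has 29 df and noncentrality gain × √30 / SD of change. If p is the chance that one arm is significant, exactly one of the two arms is significant with probability 2p(1−p).

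| Shared gain | r | p | 2p(1−p) |
|---|---|---|---|
| 0.5 SD | 0.3 | 0.609 | 0.476 |
| 0.5 SD | 0.5 | 0.754 | 0.371 |
| 0.5 SD | 0.7 | 0.927 | 0.135 |
| 0.8 SD | 0.3 | 0.947 | 0.100 |
| 0.8 SD | 0.5 | 0.989 | 0.023 |
| 0.8 SD | 0.7 | 1.000 | 0.0005 |

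**3. Between-arm power at d = 0.6.** The noncentrality is (0.6/SD) × √(30/2), with SD = 1 for the raw value, √(2(1−r)) for change and √(1−r²) for ANCOVA. The df are 58, 58 and 57.

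| r | Raw week 14 | Change | ANCOVA | ANCOVA worth, 30/(1−r²) |
|---|---|---|---|---|
| 0.3 | 0.628 | 0.489 | 0.668 | 33 per arm |
| 0.5 | 0.628 | 0.628 | 0.751 | 40 per arm |
| 0.7 | 0.628 | 0.839 | 0.892 | 59 per arm |

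The difference detectable with 80% power is 0.74 SD for the raw value and 0.70/0.64/0.53 SD for ANCOVA.

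**4. Consequence of the open choice.** Simulation of 20,000 trials per r, three visits with equal correlation r:

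- At d = 0.6, raw and change analyses at week 14 disagree on significance in 32%/31%/34% of trials.
- With no true difference, choosing raw or change at week 14 after seeing the results gives 8.6%/9.1%/9.5% false positives per outcome.
- Choosing among raw or change at week 4 or week 14 gives about 16%.

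**5. Whether another item fills the gap.** Item c checks homogeneity before the intervention and compares no results. Item e adjusts for characteristics that exclude the pre-surgery outcome. Item g names nothing. None supplies a visit, a metric or a baseline adjustment for the comparison in item d.

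**The case against.** The best defence is that item d is compressed wording. Each branch may pair a within-arm test (related-samples t, or Wilcoxon read as signed-rank) with a between-arm test (ANOVA, or Mann-Whitney U), matching the two independent variables of group and time. On that reading the SAP contains a correct between-arm test: with two arms, one-way ANOVA gives the same p-value as the independent t-test. This stands, and it is why the point is not that a valid test is absent. But the text assigns the related-samples test to the comparison of both groups, and the charitable reading still leaves visit, metric and baseline handling open.

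A second objection is that pairing subjects arbitrarily across arms would do little numerical harm. In simulation the type I error stays at 0.048 to 0.052 and power drops by about 1 to 2 points. This also stands. The objection to such a test is that its result depends on an arbitrary pairing and that equal arms are unlikely, not that it inflates error.

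Third, the within-arm figures depend on the assumed gain and become small at 0.8 SD. They matter only if two within-arm p-values are contrasted, which the plan neither proposes nor rules out. The 16% figure needs week-4 data and a post hoc choice. For the modified Harris scale, whose week-4 measurement is unclear, only the figures for a single visit are secure.

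Finally, an unadjusted comparison at a fixed visit is valid, so baseline adjustment is a matter of efficiency, and section 2 hints at change as the metric. Both are true. A hint in the design aim does not fix the analysis.

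**Conclusion.** The concern holds. As written, item d names a test that does not suit independent arms, and it leaves the valid tests without a visit, a metric or a rule for the pre-surgery value. It should be fixed before analysis. It is not fatal, because ANOVA and Mann-Whitney U are also named.

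The main cost is the undefined analysis. At 30 per arm and d = 0.6 SD, power runs from 49% to 89% across the permitted readings and baseline-adjusted ANCOVA, and two natural readings disagree in about a third of trials. If the choice followed the data, the false-positive rate would be about 9% per outcome at one visit and about 16% over two. These sizes rest on assumed correlations, gains and effect. The defect in the wording does not depend on them.

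**What to change.** Rewrite item d:

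- Remove the related-samples test from the between-arm comparison.
- For each continuous outcome, estimate the between-group difference at week 14 (and at week 4 where measured) by ANCOVA with the pre-surgery value as covariate, or by one mixed model with group, visit, group-by-visit and baseline. Report the adjusted difference with a 95% CI.
- If within-arm before-after tests are kept, list them separately and label them descriptive. State whether Wilcoxon W means the rank-sum or the signed-rank test.
- Reconcile the visits for the modified Harris scale. Section 5.2 says "The patient will be evaluated with this scale prior to the surgical intervention and 14 weeks after the surgery", while section 8, step F, says "The evaluation described in section B and C is repeated 4 weeks after surgery to subjects of both groups", and step B of that evaluation includes the scale. The visits in the model depend on the answer.

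The cost is SAP wording only. The pre-surgery values are already collected, no visit is added, and ANCOVA is already named in item e.

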1. OBJECTIVES

The objectives of our study are the following:

General:

- Determine the effectiveness of a protocolized treatment of specific physiotherapy for patients undergoing femoroacetabular syndrome by means of arthroscopy in pain, range of mobility and functionality.

Specific:

- Check how the age, level of physical activity prior to the study, sex, level of adherence to the program or body mass index of the subject influences the effectiveness of protocolized treatment of physiotherapy in patients surgically operated on femoroacetabular syndrome by arthroscopy.

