- Standing patient, hip extension with knee in full extension with resistance in the ankle with an elastic band of 1.5 m in length and medium resistance (4 sets of 10 repetitions twice a day)
- Standing patient, hip extension with knee in flexion of 45° with resistance in the ankle with an elastic band of 1.5 m in length and medium resistance (4 sets of 10 repetitions twice a day)
- Standing patient, hip extension with knee in 90° flexion with resistance in the ankle with an elastic band of 1.5 m in length and medium resistance (4 sets of 10 repetitions twice a day)
- Patient sitting and full knee extension with resistance in the ankle with an elastic band of 1.5 m in length and medium resistance (4 sets of 15 repetitions twice a day).
- Basic stretching of quadriceps, hamstrings, adductor and abductor (3 times a week).

Avoid climbing stairs, ramps, squats, forced hip flexion and crossing legs in all phases.

To check the adherence to the treatment, measures based on self-report of the subject

will be used since they are the easiest to obtain and the most frequently used to measure the adherence. The measuring instrument used will be the completion of a diary design for this purpose. It will be used to monitor the performance and duration of the protocol exercises. Through the data obtained in this diary, the overall percentage of therapeutic adherence on the recommended behavior will be determined. This system acts as a reminder increasing the probability of compliance with the work plan.

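### The specific objective asks what modifies the protocol's effect, but SAP items e and g specify no group-by-characteristic interaction, so a merely prognostic factor may be reported as a modifier

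*Combined protocol and SAP*

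**What the plan says.** Section 1 (Objectives) has one general objective, the protocol's effectiveness "by means of arthroscopy in pain, range of mobility and functionality". Its one specific objective is to check how age, prior physical activity, sex, "level of adherence to the program or body mass index of the subject influences the effectiveness" of the protocol.

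Two items of the SAP's Inferential analysis bear on the specific objective:

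- Item e: "Chi square test or ANCOVA to analyze the influence of the general characteristics of the sample on the effect of the intervention".
- Item g: "Regression analysis using the multiple linear model to study the relationship between sets of variables".

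Neither item gives an outcome, time point, model formula or product term, and no interaction or subgroup contrast appears elsewhere.

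Section 5.1 lists the general characteristics as age, BMI, sex, weekly sports hours, "orthopedic surgeon who performed the intervention and compliance with the program". On adherence, section 4 (Intervention protocol) relies on "measures based on self-report of the subject" and names no arm. Section 8 (Study sequence), step E, says of the intervention group that "they will have to follow a physiotherapy exercise plan at home whose compliance they will have to register in an activity diary". No diary is described for controls.

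**The concern.** Effectiveness is a contrast between intervention and control. A characteristic influences effectiveness only if that contrast differs across its values, and a group-by-characteristic interaction estimates exactly this. Item e's wording shows the same intent, but the tests it names do not deliver it as written. A chi-square of characteristic against outcome tests marginal association. In an equal-slopes ANCOVA the covariate coefficient says whether the characteristic predicts outcome in both groups alike.

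The only specific objective is at stake. Age, BMI or activity may well predict recovery after hip arthroscopy whatever the physiotherapy. If that prognostic signal is read as the answer, the report would say that the protocol works better or worse in certain patients when nothing of the kind has been shown.

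A secondary concern, held with moderate confidence, is that adherence is listed beside baseline characteristics although it arises after randomisation and its recording in controls is not stated.

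**Working it through.** **Inputs.** From the SAP: around 30 per group (a feasibility figure; the final size is to come from a 10-subject pilot) and p < 0.05, taken as two-sided. From section 2: 1:1 allocation. The documents give no effect size, SD or prognostic strength, so those below are assumptions shown over a range. For the same reason, 30 per group cannot be reproduced from a calculation. Back-solving, it gives 80% power for a main effect of 2.80 × √(2/30) = 0.72 SD.

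**Step 1. A purely prognostic continuous factor.** Model: outcome = 0.5 × group + 0.5 × baseline + r × factor + √(1 − r²) × error, with factor, baseline and error standard normal and no true interaction. Here r is the baseline-adjusted association. The within-group variance is 1.25, so the marginal correlation is r/1.118. The table gives the share of simulated trials with p < 0.05.

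| r | Equal-slopes covariate term, baseline in model | Same, without baseline | Interaction term |
|---|---|---|---|
| 0 | 5% | 5% | 5% |
| 0.1 | 11–12% | 11% | 5% |
| 0.2 | 33% | 27% | 5% |
| 0.3 | 64% | 55% | 5% |
| 0.4 | 89% | 80% | 5% |
| 0.5 | 98% | 96% | 5% |

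An approximate hand check at r = 0.3: the expected test statistic is 0.3/√(1 − 0.09) × √60 = 2.44, which gives power near 68%. That is slightly above the simulated 64% because it ignores the degrees of freedom used and the randomness of the factor.

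**Step 2. Four characteristics, one prognostic and none a modifier.** With the prognostic factor at r = 0.1, 0.2, 0.3, 0.4 and 0.5, at least one covariate term is significant in about 24%, 43%, 69%, 90% and 99% of trials. For four interaction terms the figure is 18–19%, in line with 1 − 0.95⁴ = 18.5%.

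**Step 3. Chi-square.** Take a factor splitting 60 patients into 30 and 30, with positivity of 20% against 40%, 50% or 60%, the same in both treatment groups. The uncorrected test is significant in about 39%, 70% and 90% of trials. With continuity correction the rates are about 30–31%, 60–62% and 85%. The plan does not say which form would be used.

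**Step 4. What the interaction term can and cannot do.** For a 50:50 factor there are four cells of 15, so the SE of the interaction is SD × √(4/15) = 0.516 SD. Then 80% power needs 2.80 × 0.516 = 1.45 SD. At 0.72 SD, t-based power is about 28%. Adjusting for a baseline correlated 0.5 with outcome reduces 1.45 to 1.45 × √0.75 = about 1.25 SD. Where modification is in one arm only (slopes 0 v 0.3, 0.4, 0.5), the covariate term is significant in 21%, 33% and 48% of trials and the interaction in 21%, 33% and 49%, so no power is gained. At 0.1 v 0.5 the figures are 64% and 35%. Only with exactly opposite slopes (±0.3 to ±0.5), an extreme case, does the covariate term nearly always miss a modifier: 6–8% v 62–98%.

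**Step 5. Number of tests.** Four characteristics × one outcome = 4. Four × eight (VAS, modified Harris, six ROM measures) = 32, or 32 × 0.05 = 1.6 expected false positives. Each binary orthopaedic test adds 4, so all three would bring 32 to 44 (44 × 0.05 = 2.2 expected).

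**Step 6. Adherence.** Within about 30 intervention patients, 80% power needs a correlation of tanh(2.80/√27) = 0.49.

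**The case against.** The strongest reply is that item e already speaks of influence on the intervention's effect, and that ANCOVA and item g's multiple regression can both hold a product term; the analyst may intend exactly that. This stands in part. A reader might infer that the sponsor has planned to treat prognosis as modification, or that the chosen methods are incapable. The documents support neither. They neither state nor rule out the misreading, and only the ordinary chi-square is unable to answer the question. What remains is that the one term answering the objective is unspecified and that one of the two tests named for it cannot supply it.

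A second reply is that the error rates depend on assumed prognostic strength. They do: at 0.1 the covariate term misleads in only about 11% of trials. A reader should not conclude that a false modifier will be reported, only that it may be.

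Third, the practical gain is modest because interaction power is poor at this size. That is correct. It argues for labelling the results exploratory, not for leaving the term out.

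Fourth, the adherence paragraph sits in the intervention section and refers to the protocol's exercises, which suggests an intervention-only diary. That is plausible, and it makes a group-by-adherence comparison less feasible still.

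**Conclusion.** The point holds as under-specification with a concrete consequence. The specific objective needs a group-by-characteristic interaction, and the plan names none. If the equal-slopes covariate term is read as the answer, a purely prognostic factor is flagged as a modifier in about 11% to 98% of trials over associations of 0.1 to 0.5, against about 5% with the interaction. If the chi-square is read that way, the rates are 39% to 90% uncorrected, or about 30% to 85% corrected, over the positivity contrasts assumed.

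The sizes rest on 30 per group and on assumed prognostic strengths; the direction does not depend on the strength, provided it is not zero. A reader might also infer that the interaction term makes true modifiers easier to find. In general it does not. Its benefit is correct interpretation and control of false positives.

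Confidence is high for the missing term and moderate for the adherence part. The sponsor should make the change.

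**What to change.** Rewrite item e as follows.

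- Designate one continuous outcome before analysis. Fit a baseline-adjusted ANCOVA at 14 weeks with group, characteristic and group-by-characteristic interaction, one model each for age, sex, BMI and prior weekly activity. Week 14 is the end of the programme, when all outcomes are measured.
- Do not rest the choice of 14 weeks on the Harris schedule. Section 5.2 says "The patient will be evaluated with this scale prior to the surgical intervention and 14 weeks after the surgery", whereas section 8 (steps B and F, and the rule on deterioration) places that scale at 4 weeks too. These passages must be reconciled.
- Do not use chi-square for this objective. If Fabere, Faddir and, if scored positive or negative, Ober are examined, use logistic models with the same interaction. Expect little precision: at 30% positivity the 95% CI for the ratio of odds ratios runs about 10-fold either way.
- Report interaction estimates with 95% CIs as exploratory, with the number of tests: 4 for one outcome, 32 for VAS, Harris and six ROM measures, plus 4 per binary test.
- State that item g does not replace these models, and whether surgeon, which section 5.1 lists but the objective does not, is for adjustment only.
- Keep compliance out of between-group models. Report it as a descriptive association within the intervention group, align the adherence part of the objective, and state whether controls keep a diary.

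The cost is SAP wording, a few model terms and one amended objective, with no new data. The price in inference is low interaction power (about 28% at 0.72 SD) and an adherence result that is descriptive only.

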The sample will be divided into 2 groups: Intervention Group and Control Group. The postoperative physiotherapeutic treatment protocol described will be applied to the intervention group. The non-intervention group will receive the nonspecific protocol of postoperative treatment for hip rehabilitation described by Gocen et al.

7. EVALUATION.

The evaluator is the person who will perform the pre and postsurgical measurements. He will be trained in the use of the goniometer and in the performance of orthopedic tests as well as in the material to be used. It will be located in the "Evaluation Room", with the material and conditions necessary to carry out the measurements. It will register and store the data for its later evaluation and statistical analysis.

The evaluator will be blinded with respect to the subject's belonging to the intervention or control group.

Data will be recorded at three times: before surgery, after 4 weeks and after 14 weeks of surgery. Immediate postoperative measurements will not be made, given that the clinical picture and tissue injury of the intervention could cause inaccurate results because a period of post-surgical wound stabilization has not elapsed.

These tests and measurements of variables will provide us with the degree of hip readjustment and its functionality, since they respond to the affected musculoskeletal structures both prior to the arthroscopy intervention due to the pathophysiology of the FAI, and after it for the wounds and surgical scars that are generated.

8. STUDY SEQUENCE.

A. Recruitment: it takes place before the surgery in the Traumatology clinic of Alicante Clinic (we attach authorization of the center to carry out the study) Two facultative specialists in orthopedic surgery and traumatology, transfer the information to the patient in written support about the characteristics of the study , purpose and form of follow-up, at the same time that they verify the eligibility of the subject according to the criteria of the study. Another member of the research team will independently check the eligibility of the subject in an evaluation session and will be responsible for performing the evaluations of the study variables before surgery, at 4 and 14 weeks after surgery. The evaluator will be present to resolve and clarify any doubts in this regard. After this, and with the acceptance of the patient to be part of the study, the informed consent will be signed.

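### SAP item f plans Cronbach's alpha as the only reliability index for the measuring tools; for everything except the modified Harris scale the result would be undefined or uninterpretable

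*Combined protocol and SAP*

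**What the plan says.** The Inferential analysis list of the SAP gives the whole reliability plan in item f: "For the reliability analysis of the measuring tools, Cronbach's alpha test will be used". It does not say which tools are meant, what would serve as the items, or at which visit the coefficient would be computed.

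The tools are set out in section 5.2 of the protocol:

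- **Range of mobility.** "In the present study measurements will be made by goniometry of hip joint movement ranges", in six directions, each in degrees.
- **Orthopaedic tests.** FABERE and FADDIR are read as positive or negative according to whether pain is reproduced. No scoring rule is given for Ober. Published reliability is cited for FABERE ("Test with inter-evaluator reliability in Kappa values (95% CI) of 0.60"), FADDIR ("Test with inter-evaluator reliability in Kappa values of 0.48") and Ober ("Test with inter-evaluator reliability of 0.90", coefficient not named).
- **Pain.** A VAS: "It is a continuous quantitative variable with a range between 0 and 10".
- **Function.** "The modified Harris Scale will be used to the patient to evaluate the functionality of the hip". Section 8, step B, calls it a questionnaire.

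On who measures and when, section 7 states: "The evaluator is the person who will perform the pre and postsurgical measurements". Measurements are made before surgery and at 4 and 14 weeks after it. The sequence in section 8, step B, lists each movement and each test once. Neither section mentions a second rater, a repeat reading in the same session or a test-retest sub-study.

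**The concern.** Alpha answers one question: how far several items, meant to capture the same construct, vary together. The reliability of a goniometer reading, a pain score or a provocation test is a different question: how closely a repeat of the same measurement would agree with the first. That needs repeated measurements of the same thing while the patient's state is unchanged, and the plan describes none.

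An analyst following item f would therefore have to find items somewhere. The data offer only the different movements or tests within a visit, or the same measurement across the three visits. Neither is a replicate. The plan also departs from its own measurement section, which cites kappa for two of the three tests.

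What is at stake is a reliability figure for range of mobility or pain, both named in the general objective, that does not describe the measurement error of those outcomes.

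**Working it through.** The plan states no alpha value, so there is no figure to reproduce. The check asks what alpha would return for each tool on the data described. All SDs and correlations below are assumptions for illustration; the documents give none.

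**Formula.** For k items, alpha = k/(k − 1) × (1 − sum of item variances / variance of the item sum). If all items have equal variance and common correlation ρ, this becomes kρ / (1 + (k − 1)ρ).

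**1. VAS within a visit.** There is one score, so k = 1 and k/(k − 1) divides by zero. Alpha does not exist.

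**2. Three visits as items, error-free instrument.** Assume a baseline SD of 10 degrees and independent true changes with SD s at each of the two later visits.
- Item variances: 100, 100 + s², 100 + s²; their sum is 300 + 2s².
- Variance of the item sum: 900 + 2s².
- Alpha = 1.5 × 600 / (900 + 2s²) = 900 / (900 + 2s²).

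| s (degrees) | Alpha |
|---|---|
| 0 | 1.00 |
| 5 | 900/950 = 0.95 |
| 10 | 900/1100 = 0.82 |
| 15 | 900/1350 = 0.67 |

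There is no measurement error in this example. Every value below 1 comes from patients truly recovering by different amounts.

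**3. Six movements, or three tests, as items, each error-free.**

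| ρ | Six movements | Three tests |
|---|---|---|
| 0 | 0.00 | 0.00 |
| 0.1 | 0.6/1.5 = 0.40 | 0.3/1.2 = 0.25 |
| 0.3 | 1.8/2.5 = 0.72 | 0.9/1.6 = 0.56 |
| 0.5 | 3.0/3.5 = 0.86 | 1.5/2.0 = 0.75 |

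The instrument is perfect throughout. The coefficient tracks only how strongly the different movements or tests are correlated.

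**4. If two goniometer readings per visit were added and alpha kept.** Assume a true SD of 10 degrees and an error SD of 5 degrees.
- Single-reading reliability: 100/(100 + 25) = 0.80.
- Alpha for two readings: 2 × 0.80/(1 + 0.80) = 0.889, which is the consistency of the average of the two.
- With a 10-degree systematic shift between the readings, alpha stays at 0.889. The shift adds a between-reading variance of 10²/2 = 50, so the absolute-agreement ICC for one reading falls to 100/(100 + 25 + 50) = 0.57.

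Here alpha lies above the reliability of a single reading and does not register the shift. In steps 2 and 3 it lies below the true reliability of 1. The error has no fixed direction.

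**The case against.** Several points can fairly be made for the plan.

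- **The scope of item f is not spelled out.** The text does not say that alpha is for every tool, and it could be read as meant for the Harris questionnaire, where alpha may be suitable. That reading is possible but less natural, because item f speaks of measuring tools in the plural and without limit. The proposed rewording settles it either way.
- **The number of goniometer readings is not stated.** If replicates are in fact taken, alpha is a legitimate consistency coefficient for their mean. This stands. Even so, step 4 shows that it would not describe a single reading or reveal a shift between readings.
- **The item is ancillary.** Reliability is not a study objective, and items d, e and g do not use its result. This stands and limits the weight of the point.

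Two stronger readings are tempting, and the documents support neither. A reader might infer that alpha always overstates reliability. The usual step-up formula, applied to an assumed single-reading reliability of 0.50 to 0.60, gives 0.75 to 0.82 for three items and 0.86 to 0.90 for six. That arithmetic treats visits or movements as parallel repeats of one quantity, which they are not, and the starting values come from nowhere in the documents. Steps 2 and 3 show alpha falling below the true reliability. A reader might also infer that the sponsor will use the figure to vouch for the range-of-mobility and pain outcomes. No section says how the result of item f will be used.

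**Conclusion.** The point holds as a correction to an ancillary item. As written, item f yields no value for the VAS within a visit. For goniometry and the orthopaedic tests it yields a value that reflects correlation between constructs, or differences in recovery. Only the modified Harris scale is a plausible use.

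The size cannot be given as a bias in one direction. Under the assumed SDs, an error-free instrument would show 0.67 to 0.82 over three visits (true-change SD 15 and 10 degrees, baseline SD 10). Over six movements it would show 0.00 to 0.86 for correlations of 0 to 0.5. The exact values depend on these assumptions; the conclusion that the figure is uninterpretable does not. It does rest on reading item f as covering all the tools, and on there being no replicate readings, since none is described. The between-group comparison is not affected.

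**What to change.** Reword item f so that Cronbach's alpha applies only to the item scores of the modified Harris scale. State that no study-derived reliability claim will be made for goniometry, the VAS or the orthopaedic tests. This changes one SAP line. The item-level Harris scores must be kept as well as the total. The downside is fewer reliability figures to report.

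If the sponsor does take replicate readings, report an absolute-agreement ICC with the standard error of measurement for goniometry, and kappa for the orthopaedic tests. Three limits apply:

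- With one evaluator the results are intra-rater only and should be labelled so. They are not comparable with the inter-evaluator values cited in section 5.2, they would not reveal a bias common to all that evaluator's readings, and the second reading is taken with the first one known.
- Duplicate goniometry leaves the VAS without a reliability estimate.
- The sample size section of the SAP lets the 10 pilot subjects join the final sample only if neither the protocol nor the measured variables change. Check that condition before adding readings.
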